8.3.4. Clinical Safety Laboratory Assessments

All protocol-required laboratory assessments must be conducted in accordance with the laboratory manual and the Schedule of Assessments. See Section 10.2 for the list of clinical laboratory tests to be performed and the Schedule of Assessments for the timing and frequency. Repeat or unscheduled samples may be taken for safety reasons or for technical issues with the samples.

The clinical significance of test results will be evaluated as follows:

- At Week 24 of Study URO-901-3005, the investigator or physician subinvestigator will assess the clinical significance of any values outside the reference ranges provided by the laboratory, and subjects with abnormalities judged to be clinically significant will be excluded from the study.
- The investigator or physician subinvestigator must review the laboratory report, document this review, and record any clinically relevant changes occurring during the study in the AE section of the eCRF. The laboratory reports must be filed with the source documents. Laboratory abnormalities associated with the underlying disease are not considered clinically significant unless judged by the investigator to have worsened or be more severe than expected for the subject's condition.
- All laboratory tests with values considered clinically significant during participation in the study or within 21 days after the last dose of study drug should be repeated until the values return to normal or baseline or are no longer considered clinically significant by the investigator or the Sponsor's designated Medical Monitor.
 - If such values do not return to normal/baseline within a period of time judged reasonable by the investigator, the etiology should be identified and the Sponsor's designated Medical Monitor notified.
 - If laboratory values from nonprotocol specified laboratory assessments performed at the institution's local laboratory require a change in subject management or are considered clinically significant by the investigator (eg, SAE or AE or dose modification), then the results must be recorded in the eCRF.

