If **any** of the following liver test abnormalities develop, Study Treatment should be withheld immediately with appropriate clinical follow-up (including repeat laboratory tests, until a subject's laboratory profile has returned to normal/baseline status), and the event reported as an SAE:

- ALT or AST > 8 x upper limit of normal (ULN)
- ALT or AST > 5 x ULN and persists for more than 2 weeks
- ALT or AST > 3 x ULN and total bilirubin > 2 x ULN or international normalized ratio (INR) > 1.5
- ALT or AST > 3 x ULN with appearance of fatigue, nausea, vomiting, right upper quadrant pain or tenderness, fever, rash and/or eosinophilia (> 5%)

Rechallenge may be considered if an alternative cause for the abnormal liver tests (ALT, AST, total bilirubin) is discovered and the laboratory abnormalities resolve to normal or baseline values. The investigator and Sponsor's designated Medical Monitor must discuss and agree with any decision to rechallenge.

Rechallenge should not occur when the etiology of the liver test abnormalities is considered possibly drug induced.

8.4.6.2. Criteria for Permanent Discontinuation of Study Treatment in Association with Liver Test Abnormalities

Study treatment should be discontinued permanently if **all** of the following 4 criteria are met (ie, potential severe drug-induced liver injury/Hy's law case):

- Total bilirubin increases to $> 2 \times$ ULN or INR > 1.5 **and**
- AST or ALT increases to $\geq 3 \times$ ULN **and**
- Alkaline phosphatase value does not reach $2 \times$ ULN **and**
- No alternative cause explains the combination of the above laboratory abnormalities; important alternative causes include, but are not limited to the following:
 - Hepatobiliary tract disease
 - Viral hepatitis (eg, hepatitis A/B/C/D/E, Epstein-Barr virus)
 - Exposure to hepatotoxic agents/drugs or hepatotoxins, including herbal and dietary supplements, plants, and mushrooms
 - Alcoholic hepatitis
 - Non-alcoholic steatohepatitis
 - Autoimmune hepatitis

If an alternative cause for hepatotoxicity is identified, then it should be determined (based on the severity of the hepatotoxicity or event) whether study drug should be withheld or permanently discontinued as appropriate for the safety of the subject, following consultation with the Sponsor's designated Medical Monitor.

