9.4.2. Safety Analyses

Safety analysis will be conducted using the SAF-Ext population and summarized by the Vibegron treatment group. The treatment-emergent period will be defined as the period of time from the first dose date of vibegron in this study through 21 days after the last dose of treatment, or the date of initiation of another investigational agent or surgical intervention, whichever occurs first. Safety will be assessed through summaries of adverse events, the frequency of treatment discontinuation due to adverse events, and clinical laboratory evaluations.

AEs will be coded using the latest version of MedDRA (20.0 or higher). The severity of all adverse events will be evaluated by the Investigator. The incidence of adverse events will be presented by system organ class and preferred term, relationship to study treatment and severity.

Laboratory data will consist of chemistry, hematology and urinalysis data. Only data collected by the central laboratory will be included in the analysis.

Descriptive statistics of observed values and change from baseline for vital signs and post void residual urine volume will be listed and summarized.

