10.2. Appendix 2: Clinical Laboratory Tests

The tests detailed in Table 10-1 will be performed by the central laboratory chosen by the Sponsor. Subjects do not need to fast prior to laboratory testing. A sample for urinalysis (including microscopy for RBCs, WBCs, epithelial cells, and bacteria) and urine culture will be sent to the central laboratory only if the urine dipstick tests positive for the presence of leukocytes, nitrites, or blood cells. If a subject reports symptoms suggestive of a urinary tract infection at any visit, a urine dipstick should be performed as needed, and a sample will be sent out for urinalysis and culture and sensitivity testing.

Table 10-1 Clinical Laboratory Tests

Hematology	Chemistry	Urinalysis ^a	Other
Hematocrit	Albumin	Blood	Coagulation INR/PT/APTT ^d
Hemoglobin	Alkaline phosphatase	Glucose	
Platelet count	ALT	Protein	
WBC (total and differential)	AST	Specific gravity	
RBC	Bicarbonate	Microscopic exam (RBCs, WBCs, epithelial cells and bacteria)	
	Calcium	pH	
	Chloride	Color	
	Creatine ^b		
	Glucose (fasting or non-fasting)		
	Potassium		
	Sodium		
	Total bilirubin		
	Direct bilirubin ^c		
	Blood urea nitrogen		
	Total cholesterol		

ALT = alanine aminotransferase; APTT = activated partial thromboplastin time; AST = aspartate aminotransferase; eGFR = estimated glomerular filtration rate; INR = international normalized ratio; PSA = prostate-specific antigen; PT = prothrombin time; RBC = red blood cell count; WBC = white blood cell count

^a A sample for urinalysis and urine culture/sensitivity will be sent to the central laboratory only if the urine dipstick performed at the site is positive for the presence of leukocytes, nitrites, or blood cells.

^b eGFR will be calculated and reported by the central lab.

^c If total bilirubin is elevated above the upper limit of normal.

^d Only upon request from Principal Investigator (if ALT, AST and bilirubin are increased).

10.3. Appendix 3: Adverse Events: Definitions and Procedures for Recording, Evaluating, Follow-up, and Reporting

AE Definition

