7.4. Laboratory Evaluations

All continuous laboratory parameters will be summarized descriptively by absolute value at each visit together with the corresponding changes from baseline. All parameters will be summarized in SI units.

The number and percentage of subjects with laboratory measurements outside of the central laboratory normal range will also be summarized by visit. Shift tables from baseline to maximum post-baseline value, to minimum post-baseline value, last post-baseline value, and at each post-baseline visit will be provided for hematology and chemistry parameters to display low, normal, high, and missing values by treatment group in a 3-by-3 contingency table. Denominators for percentages will be the number of subjects with non-missing data at the specific assessment and baseline.

ALT/AST and Total Bilirubin will be displayed as eDISH plots. Maximum post-baseline total bilirubin will be presented (<2 and ≥ 2 x ULN) and plotted against maximum post-baseline ALT (<3 , ≥ 3 - <5 , ≥ 5 - <10 , and ≥ 10 x ULN), expressed as multiples of ULN. This will be repeated to show maximum post-baseline total bilirubin against maximum post-baseline AST.

Data for subjects with ALT or AST ≥ 3 x ULN, and bilirubin ≥ 2 x ULN will be presented, which will include all visits for this subset of subjects. A line plot of liver biochemistry test results (including ALP, ALT, AST, total bilirubin, and GGT) over time will also be presented for this subset of patients.

A sample for the urinalysis and urine culture will be sent to the central laboratory only if the urine dipstick performed at the site tests positive for the presence of leukocytes, nitrites, or blood cells. Central urinalysis data will be provided only in the listing.

Any data outside the central laboratory normal reference ranges will be explicitly noted on the listings that are produced.

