11.1.2. Output Figures

Table 10: List of Output Figures

Title		Population	Programming notes
Efficacy Endpoints			
14.2.1.1	Plot of LS Means (SE) of Change from Baseline in Average Daily Number of Micturition Episodes (MMRM)	FAS-Ext	Including all visits
14.2.2.1	Plot of LS Means (SE) of Change from Baseline in Average Daily Number of Urgency Episodes (MMRM)	FAS-Ext	Including all visits

Title		Population	Programming notes
14.2.3.1	Plot of LS Means (SE) of Change from Baseline in Average Number of Nocturia Episodes per Day (MMRM)	FAS-Ext	Including all visits
14.2.4.1	Plot of LS Means (SE) of Change from Baseline in Average Number of Urge Urinary incontinence Episodes per Day (MMRM)	FAS-Ext-I	Including all visits
14.2.5.1	Plot of LS Means (SE) of Change from Baseline in International Prostate Symptom Score (IPSS) Storage Score (MMRM)	FAS-Ext	Including all visits
14.2.6.1	Plot of LS Means (SE) of Change from Baseline in Volume Voided per Micturition (MMRM)	FAS-Ext	Including all visits
Safety Endpoints			
14.3.3.1	Scatter Plot of Maximum ALT Post-Baseline versus Maximum Total Bilirubin Expressed as Multiples of ULN	SAF-Ext	
14.3.3.2	Scatter Plot of Maximum AST Post-Baseline versus Maximum Total Bilirubin Expressed as Multiples of ULN	SAF-Ext	
14.3.3.3	Line Plot of Liver Chemistry Test Results over Time for Subjects with Elevated ALT or AST, and Elevated Total Bilirubin at Any Time	SAF-Ext	Only produce for subjects who potentially met Hy's law
14.3.4.1	Line Plot of Mean (SE) in CFB of Systolic Blood Pressure	SAF-Ext	X-axis starts from baseline visit
14.3.4.2	Line Plot of Mean (SE) in CFB of Diastolic Blood Pressure	SAF-Ext	X-axis starts from baseline visit
14.3.4.3	Line Plot of Mean (SE) in CFB of Pulse Rate	SAF-Ext	X-axis starts from baseline visit
14.3.5.1	Line Plot of Mean (SE) Post-Void Residual Urine Volume	SAF-Ext	X-axis starts from baseline visit, separate lines for treatment groups

Title		Population	Programming notes
14.3.6.1	Line Plot of Mean (SE) IPSS Total Scores	SAF-Ext	X-axis starts from baseline visit, separate lines for treatment groups

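### INR in the protocol's liver criteria is not systematically ascertained, and the SAP's potential Hy's law rule does not select men who qualify through INR alone

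*Protocol*

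**What the plan says.** **Criteria.** In Protocol 8.4.6.1 (temporary withholding), one of four triggers is "ALT or AST > 3 x ULN and total bilirubin > 2 x ULN or international normalized ratio (INR) > 1.5". In 8.4.6.2 (permanent discontinuation, the potential Hy's law definition), the bilirubin condition ends "ULN or INR > 1.5" and stands beside a separate condition that AST or ALT reach at least 3 x ULN. In both sections one raised transaminase is enough.

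**Availability of INR.** Table 10-1 in Protocol 10.2 puts INR, with PT and APTT, in its last column. Footnote d provides these tests "Only upon request from Principal Investigator (if ALT, AST and bilirubin are increased", with no multiple of ULN. The same appendix says "The tests detailed in Table 10-1 will be performed by the central laboratory chosen by the Sponsor", so an INR requested this way is a central result.

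**Analysis.** SAP 7.4 states: "Data for subjects with ALT or AST ≥ 3 x ULN, and bilirubin ≥ 2 x ULN will be presented". A line plot of liver tests over time is planned for the same subset. Figure 14.3.3.3 is titled by raised ALT or AST together with raised total bilirubin, and is annotated "Only produce for subjects who potentially met Hy's law". Listing 14.3.3.12 covers men who potentially met Hy's law, but no selection rule is given for it. The SAP text does not mention INR.

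**Laboratory source.** Protocol 9.4.2 states: "Only data collected by the central laboratory will be included in the analysis". Under 8.3.4, if local results change a man's management or are judged clinically significant, "then the results must be recorded in the eCRF".

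**The concern.** The criteria use INR as an alternative to bilirubin. Footnote d makes the INR depend on bilirubin being raised and, as worded, on both transaminases where the criteria need only one. The SAP then builds its Hy's law displays on bilirubin alone. A man can therefore fall out at two separate points: no INR was requested, or an INR above 1.5 was obtained but the selection rule does not use it.

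Safety is the primary objective. A transaminase elevation that requires withholding or discontinuation is a predefined AESI (Protocol 8.4.6), and SAP 7.3 tabulates it. Whether a man meets that definition can turn on INR, so incomplete ascertainment can affect the AESI count as well as the displays. An empty potential Hy's law listing would not distinguish the absence of such cases from the absence of INR results or of an INR term in the rule.

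**Working it through.** The plan states no figure on this point. The check is a comparison of the passages and a count of combinations.

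**1. Reading the criterion.** The 8.4.6.1 trigger mixes and/or without brackets. Section 8.4.6.2 separates the conditions, so I read both as: (ALT or AST raised) and (bilirubin > 2 x ULN or INR > 1.5). If INR alone were sufficient, still more men would depend on it, so this is the more cautious reading.

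**2. Combinations in which only INR can decide.** Class ALT and AST each as normal, >1 to 3, or >3 x ULN, and bilirubin as normal, >1 to 2, or >2 x ULN.
- ALT/AST pairs with at least one above 3 x ULN: 3 x 3 - 2 x 2 = 5.
- Bilirubin classes not above 2 x ULN: 2.
- Combinations that can meet this criterion only through INR: 5 x 2 = 10.

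**3. What footnote d provides for in those 10.**

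| Reading of footnote d | Calculation | INR provided for |
|---|---|---|
| ALT, AST and bilirubin all increased (literal) | 3 pairs with both transaminases raised x 1 bilirubin class | 3 of 10 |
| ALT or AST, and bilirubin, increased | 5 x 1 | 5 of 10 |
| Any one of the three increased | 5 x 2 | 10 of 10 |

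On the literal reading, 10 - 3 = 7 combinations have no provision in the footnote: bilirubin is normal, or only one transaminase is raised.

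**4. What the SAP rule selects.** It needs bilirubin at or above 2 x ULN, and all 10 combinations have bilirubin no higher than that. It selects 0 of 10 under every reading of footnote d, except where bilirubin is exactly 2 x ULN. The two gaps are therefore independent: drawing an INR in all 10 would not change the SAP subset.

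**5. Local results.** Scheduled laboratory visits after entry are Week 36 (Day 253) and Week 52 (Day 365), 365 - 253 = 112 days apart. If a liver peak in that interval is measured only locally and is clinically significant, 8.3.4 puts it in the eCRF, but the central-only rule in 9.4.2 keeps it out of the eDISH plots.

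**The case against.** A reader might infer that the INR criterion cannot be evaluated, or that no INR is drawn in a man with normal bilirubin. The documents do not support that.
- Footnote d says only that the tests are increased, so INR is provided for with bilirubin between 1 and 2 x ULN, where INR can be decisive.
- Protocol 8.3.4 allows unscheduled safety samples, and 8.4.3 obliges the investigator to arrange further tests as medically indicated or as the sponsor requests.
- The other triggers in 8.4.6.1 (ALT or AST above 8 x ULN, above 5 x ULN for more than two weeks, or above 3 x ULN with symptoms) need neither INR nor bilirubin.
- A recognised withholding event is reported as an SAE and an AESI, and so reaches those tables and listings.
- A central INR could appear in Tables 14.3.3.4 and 14.3.3.8 and Listing 16.2.3.7, if Other there means the last column of Table 10-1.
- Local values are left out of the analysis, not out of data capture. SAP 4.2.2 says collected safety data will generally be listed, so their absence from Listing 14.3.3.12 is an inference.

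All of this stands, and it limits the point to ascertainment and display. It does not remove the mismatch between footnote d and 8.4.6, because discretionary testing is not systematic testing. It also does not supply an INR term in SAP 7.4.

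A reader might also infer that leaving the protocol's alkaline phosphatase condition out of the SAP rule hides cases. It cannot: omitting a restriction only widens the screen, and SAP 7.4 already plots alkaline phosphatase.

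**Conclusion.** The point holds in a limited form. INR is not systematically ascertained where the protocol's liver criteria would use it, and the SAP's liver subset does not select a man who qualifies through INR alone. The second part does not depend on how footnote d is read: the rule reaches 0 of 10 INR-dependent combinations, apart from the boundary case. The first part does: 3, 5 or 10 of 10. None of these counts says how often such a man would occur, and the documents give no basis for a rate. SAP Section 9, which records changes from the protocol, does not mention that the liver rule is narrower than the protocol's criteria.

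Assumptions: the grouping of and/or in step 1; that Listing 14.3.3.12 follows the SAP 7.4 rule, which the SAP does not state; and that the ascertainment gap concerns the extension only. The SAP pools parent-study data after first vibegron dose, and the parent study's laboratory panel is not in these documents.

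This is worth correcting before database lock. It does not mean that recognised liver events go unreported.

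**What to change.** 1. **Protocol.** Footnote d of Table 10-1 and Sections 8.4.6.1 and 8.4.6.2 must be reconciled. Which testing rule is right is a clinical matter on which this review takes no position.
2. **SAP selection rule.** In SAP 7.4, Listing 14.3.3.12 and Figure 14.3.3.3, select subjects by the protocol's own definition: the ALT or AST criterion with bilirubin or, where a result exists, INR > 1.5. State the rule explicitly for the listing. Report how many subjects met the transaminase criterion and had no INR, so that an empty listing can be interpreted.
3. **Local results.** In the Hy's law listing and the eDISH display, include clinically significant local liver results already in the eCRF, as multiples of the local ULN and flagged as local. Keep the central-only rule for by-visit summaries and shift tables, and reword Protocol 9.4.2 or record the exception in SAP Section 9.

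The cost is SAP wording and minor programming. Local values come from different assays and reference ranges, which the flag makes visible. Protocol 8.3.4 requires the local result in the eCRF but does not mention the local reference range; where that range is missing, the value can be listed but not plotted as a multiple of ULN.

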
d. Results in persistent disability/incapacity
 
 • The term disability means a substantial disruption of a person's ability to conduct normal life functions. • This definition is not intended to include experiences of relatively minor medical significance such as uncomplicated headache, nausea, vomiting, diarrhea, influenza, and accidental trauma (eg, sprained ankle) which may interfere with or prevent activities of daily living but do not constitute a substantial disruption.

e. Is a congenital anomaly/birth defect

f. Other situations:
 
 • Medical or scientific judgment should be exercised in deciding whether SAE reporting is appropriate in other situations such as important medical events that may not be immediately life threatening or result in death or hospitalization but may jeopardize the subject or may require medical or surgical drug to prevent one of the other outcomes listed in the above definition. These events should usually be considered serious. 
Examples of such medically significant events include invasive or malignant cancers, intensive treatment with a drug in an emergency room or at home for allergic bronchospasm, blood dyscrasias or convulsions that do not result in hospitalization, or development of drug dependency or drug abuse.

Recording and Follow-Up of AEs and SAEs**AE and SAE Recording**

- When an AE or SAE occurs, it is the responsibility of the investigator to review all documentation (eg, hospital progress notes, laboratory reports, and diagnostics reports) related to the event.
- The investigator will then record all relevant AE or SAE information in the eCRF.
- All SAEs (including serious AESIs) must be **reported in the eCRF within 24 hours of the study site personnel's knowledge of the event**, regardless of the investigator assessment of the relationship of the event to study drug.
 - The event term, start date, severity, and initial causality assessment must be entered in the AE eCRF page and the event must be marked as "Serious". This will activate additional assessment fields including "action taken with study drug", "seriousness criteria", and "brief description" which should be completed as soon as information is available. Marking the event as "serious" will automatically send required notifications for Sponsor or designee review.
 - The initial SAE report should include:
 - The date of the report
 - A description of the SAE (event term, seriousness of the event, date of onset, intensity)
 - Causal relationship to the study drug
 - A discharge summary should be provided for all hospitalizations. If the subject died, the report should include the cause of death as the event term (with death as the outcome) and whether the event leading to death was related to study drug, as well as the autopsy findings, if available
- Nonserious AESIs should be reported on the eCRF within 72 hours of knowledge of the information.
- It is **not** acceptable for the investigator to send photocopies of the subject's medical records to the Sponsor or designee in lieu of completion of the AE or SAE eCRF page.
- There may be instances when copies of medical records for certain cases are requested by the Sponsor or designee. In this case, all subject identifiers, with the exception of the subject number, will be redacted on the copies of the medical records before submission to the Sponsor.
- The investigator will attempt to establish a diagnosis of the event based on signs, symptoms, and/or other clinical information. Whenever possible, the diagnosis (not the individual signs/symptoms) will be documented as the AE/SAE.

Assessment of Intensity	
1/MILD	Asymptomatic or mild symptoms, clinical or diagnostic observations only; intervention not indicated.
2/MODERATE	Minimal, local, or noninvasive intervention indicated; limiting age-appropriate instrumental activities of daily living
3/SEVERE OR MEDICALLY SIGNIFICANT	Not immediately life-threatening; hospitalization or prolongation of hospitalization indicated; disabling; limiting self-care activities of daily living
4/LIFE-THREATENING	Life threatening consequences; urgent intervention indicated
5/DEATH	Death related to adverse event

An event is defined as *serious* when it meets at least one of the predefined outcomes as described in the definition of an SAE/SADE, NOT when it is rated as severe.

Assessment of Causality

 The investigator is obligated to assess the relationship between study drug and each occurrence of each AE or SAE. A reasonable possibility of a relationship conveys that there are facts, evidence, and/or arguments to suggest a causal relationship, rather than a relationship cannot be ruled out. The investigator will use clinical judgment to determine the relationship. Alternative causes, such as underlying disease(s), concomitant therapy, and other risk factors, as well as the temporal relationship of the event to study drug administration will be considered and investigated. The investigator will also consult the Investigator's Brochure (IB) and/or product information, for marketed products, in his/her assessment. For each AE or SAE, the investigator must document in the medical notes that he/she has reviewed the AE or SAE and has provided an assessment of causality. There may be situations in which an SAE has occurred and the investigator has minimal information to include in the initial report to the Sponsor or designee. However, it is very important that the investigator always make an assessment of causality for every event before the initial transmission of the SAE to the Sponsor or designee. The investigator may change his/her opinion of causality in light of follow-up information and send an SAE follow-up report with the updated causality assessment. The causality assessment is one of the criteria used when determining regulatory reporting requirements.

Reporting of SAEs**SAE Reporting**

All SAEs must be **reported in the eCRF within 24 hours of the study site personnel's knowledge of the event**, regardless of the investigator assessment of the relationship of the event to study drug. Marking the event as "Serious" will activate additional assessment fields.

